## 9.5 DEVIATIONS

- 9.5.1 Investigators are required to adhere to the Clinical Investigational Plan, the signed Investigator's Agreement, applicable national or local laws and regulations, and any conditions required by the appropriate Ethics Committees or applicable regulatory authorities.
- 9.5.2 A **Deviation** is defined as a situation in which there is a non-compliance with the protocol.
- 9.5.3 Anticipated deviations:
  - 9.5.3.1 Patient Informed Consent is not approved by Ethics Committee;
  - 9.5.3.2 Patient Informed Consent is not signed and/or dated by the patient and/or investigator;
  - 9.5.3.3 Study specific procedure was performed before the Patient Informed Consent was signed and dated by patient;
  - 9.5.3.4 Investigational Required Visit not performed;
  - 9.5.3.5 Investigational Required Visit performed outside the visit window;
- 9.5.4 Should a deviation occur, document the information in the Deviation case report form (CRF). By completing the CRF the sponsor will be notified.

**NOTE:** When a deviation occurs after enrollment for **patient consent**, record the information in the hospital record, **immediately** document the information in the Deviation and Termination case report form (CRF). By completing the CRF the sponsor will be notified.

- Refer to appendices "Data Collection" and "Data Collection Method".
- Access the eCRF application.
- Select the scheduled or unscheduled visit to which the deviation is related.
- Enter deviation information into the Termination CRF.
  - Date of deviation

- When the deviation occurred
- Type of deviation
- Medical justification
- The CRF must be authorized by the principal investigator or delegated co-investigator.
- Submit the CRF. When the CRF is submitted, an alert is generated notifying the sponsor.

When a deviation occurs after enrollment for **patient eligibility**, record the information in the hospital record, **immediately** document the information in the Deviation case report form (CRF). By completing the CRF the sponsor will be notified. All the efforts should be made to keep the patient in the study.

The investigator must notify the EC or IRB, if appropriate, in accordance with national and local laws and regulations.

## 9.6 ENROLLMENT

- 9.6.1 Enrollment activities are performed after patients are screened and may occur prior to or at the same time as the baseline visit.
- 9.6.2 The site should maintain a Patient Screening Log, accounting for the patients who are and are not eligible for the investigation. All patients that are considered for this investigation, should be mentioned on this Patient Screening Log.
- 9.6.3 A patient who meets the inclusion criteria and does not meet the exclusion criteria is eligible to participate in the investigation.
  - 9.6.3.1 If a patient does not meet inclusion or meets exclusion criteria cannot participate in the investigation.
- 9.6.4 Inform the eligible patient about the investigation and provide the informed consent form to the patient.
  - 9.6.4.1 The process of obtaining written consent from an eligible patient needs to comply with the Declaration of Helsinki, International Standards Organization (ISO) 14155-1 and applicable local laws and regulations.
- 9.6.5 Obtain the signature and date from the eligible patient on the ethics committee (EC) approved informed consent form.
  - 9.6.5.1 If the eligible patient cannot sign and date the EC approved informed consent him/herself then refer to ISO 14155-1 regarding alternatives for obtaining signature on the informed consent.
  - 9.6.5.2 If an eligible patient does not sign and date the informed consent, s/he cannot participate in the investigation. No further protocol activities are performed.

- 9.6.6 Obtain the signature and date from the principal investigator or delegate on the ethics committee (EC) approved informed consent form.
- 9.6.7 The patient is enrolled in the investigation when both the patient and investigator signed/dated the informed consent.
  - 9.6.7.1 If there are deviations with regards to obtaining informed consent, notify the EC/IRB appropriately.
- 9.6.8 Provide one original signed and dated copy by patient and the principal investigator or delegate to the patient.
- 9.6.9 File the second original appropriately in the Investigator Study Binder (ISB).
- 9.6.10 Record enrollment information (name of the investigation, consent and inclusion/exclusion criteria) in the hospital records, complete the Enrollment Case Report Form. Every effort will be made to notify the sponsor within 5 working days of enrollment. The CRF must be authorized by the principal investigator or delegate.

9.6.10.1 Refer to "Appendix Data Collection" for access and information regarding patient data collected for this investigation.

## 9.7 BASELINE VISIT (INTERVENTION)

- 9.7.1 All Baseline activities are performed after the patient is enrolled in the investigation and no more than 30 days prior to undergoing cardiac surgery procedure.
- 9.7.2 The following information will be collected at the baseline visit either from hospital records or through patient interaction documented in the hospital records:
  - 9.7.2.1 Patient Demographics & Physical Examination
    - Collect the age;
    - Collect the gender;
    - Provide the most recent value (within the last month) of the patient height;
    - Provide the most recent value (within the last month) of the patient weight;
  - 9.7.2.2 Patient Cardiovascular History
    - Provide the most recent value (within the last month) of the New York Heart Association (NYHA) classification;
  - 9.7.2.3 Patient Anticoagulant/Antiplatelet Medication
    - Identify the Anticoagulant/Antiplatelet medications the patient is taking currently;

**9.7.2.4 Patient Medical History**

- Indicate the pre-existing cardiac conditions and cardiac procedures; and
- Indicate the relevant non-cardiac medical conditions.

**9.7.2.5 Baseline echo data (if available)**

- Provide the most recent values (within the last month) of the specified echo variables;

**9.7.2.6 Aortic Valve Replacement Information**

- Indicate the details about valve being replaced (type, etiology, pathology, ect..)

**9.7.2.7 Operative Information**

- Indicate the details about valve replacement (suture technique, implanting surgeon and experience, details about Trifecta valve implanted and concomitant procedures).

**9.7.2.8 Refer to "Appendix Data Collection" for access and information regarding patient data collected for this investigation.****9.7.3 Adverse Event (when applicable)****9.7.3.1 Check if any adverse event or adverse device effect occurred.****9.7.3.2 Report the adverse event according to specifications in section "Adverse Event".****9.8 PRE-DISCHARGE VISIT****9.8.1 The following information will be collected at the pre-discharge visit either from hospital records or through patient interaction (documented in the hospital records):****9.8.1.1 Patient Cardiac Medication**

- Provide information on cardiac medication;

**9.8.1.2 Echocardiography (if available)**

- Provide pre-discharge echo data;

**9.8.2 Record the pre-discharge information in the hospital records and complete the Follow Up Case Report Form (CRF).****9.8.3 Adverse Event (when applicable)****9.8.3.1 Check if any adverse events or adverse device effect occurred since the last visit and document this in the hospital records.****9.8.3.2 Report the adverse event according to specifications in section "Adverse Event" of the Case Report Form (CRF).****9.8.4 Patient Death (when applicable)**

- 9.8.4.1 If the patient died before hospital discharge, report it immediately to the sponsor as indicated in section "Patient Death".
- 9.8.5 Early Withdrawal (when applicable)
  - 9.8.5.1 If the patient decides to withdraw from the investigation for whatever reason, report this immediately to the sponsor as indicated in section "Early conclusion to patient participation".
- 9.8.6 Refer to "Appendix Data Collection" for access and information regarding patient data collected for this investigation.

## 9.9 PROTOCOL REQUIRED FOLLOW-UP

- 9.9.1 Scheduled visits will occur yearly over 10 years after the implant date. The follow up will occur in the outpatient department of each participating institution or, if not possible, by telephone contact with the patient.
- 9.9.2 The Follow Up schedule is summarized in Table 1.
- 9.9.3 The following information will be collected at the follow up visit either from hospital records or through patient interaction (documented in the hospital records):
  - 9.9.3.1 Provide the most recent value (within the last month) of the New York Heart Association (NYHA) classification;
  - 9.9.3.2 Patient Cardiac Current Medication
    - Provide information on cardiac medication therapy.;
  - 9.9.3.3 Echocardiography (if available)
    - Provide follow-up echo data (echo date must be in the follow-up window);
- 9.9.4 Record the follow up information in the hospital records and complete the Follow Up Case Report Form (CRF).
- 9.9.5 Adverse Event (when applicable)
  - 9.9.5.1 Check with the patient if any adverse events or adverse device effect occurred since the last visit and document this in the hospital records.
  - 9.9.5.2 Report the adverse event according to specifications in section "Adverse Event" of the Case Report Form (CRF).
- 9.9.6 Patient Death (when applicable)
  - 9.9.6.1 If the patient died before the visit took place, report it immediately to the sponsor as indicated in section "Patient Death".
- 9.9.7 Early Withdrawal (when applicable)
  - 9.9.7.1 If the patient decides to withdraw from the investigation for whatever reason, report this immediately to the sponsor as indicated in section "Early conclusion to patient participation".
- 9.9.8 Refer to "Appendix Data Collection" for access and information regarding patient data collected for this investigation.

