#### **4.2 SECONDARY ENDPOINTS**

- 4.2.1 The secondary endpoints of this investigation are:
  - 4.2.1.1 Actuarial survival rate;
  - 4.2.1.2 Freedom from valve related death;
  - 4.2.1.3 Freedom from structural valve deterioration.

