### **8.2 ENDPOINT ANALYSIS**

- 8.2.1 Non-parametric survival analysis will be used to calculate the freedom rate( $S$ ) from reoperation due to SVD at year 10 post implant and the corresponding variance ( $Var_s$ ) will be computed with Peto's formula for survival analysis. The lower bound of the 95% confidence interval for  $S$  will be calculated using the formula  $S - Z_{0.5} * (Var_s)^{1/2}$ . If the lower bound of  $S$  is bigger than or equal to 94%, then the expected estimate is confirmed. The survival time will be calculated as the number of days from implant date to reoperation date due to SVD. A Kaplan-Meier curve with the cumulative survival rate will also be presented.
- 8.2.2 A Cox regression model will be used to further investigate the effects of the factors on the primary endpoint. These factors include baseline factors such as learning curve (1, 2, 3, >3), age, gender, NYHA Class etc..

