### **8.3 ADDITIONAL DATA**

- 8.3.1 For the time to event data, survival analysis will be used to estimate the survival rate and 95% confidence interval, and a Kaplan Meier curve will also be presented.
- 8.3.2 Continuous data will be summarized with mean, standard deviation, median and range. Frequency and percentage will be reported for all categorical data.

---

 Reference : Alan B cantor , SAS survival analysis techniques for medical research

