## 9 PROTOCOL DESCRIPTION

### 9.1 PROTOCOL PROCEDURES - OVERVIEW

Table 1 – Protocol Procedure Overview

These activities are applicable to all patients.

(\*) This is only when available

(\*\*) This is **only to be performed when applicable.**

	When	Window	Activities
Pre-Intervention		Not Applicable	
 
• Patient Eligibility
 
• Patient Informed Consent
 
• Patient Demographics & Physical Examination
 
• Patient Cardiovascular History
 
• Patient Current Cardiac Medications
 
• Patient Medical History
 
• Echo (*)
 

Intervention (+baseline)		Not Applicable	
 
• Aortic Valve Replacement Information
 
• Operative Information
 
• Adverse Events(**)
 
• Echo (*)
 

Pre-discharge		Not Applicable	
 
• Patient Current Cardiac Medications
 
• Adverse Events(**)
 
• Echo (*)
 

Yearly follow-up	Yearly	<30 days >61 days	
 
• Patient Current Cardiac Medications
 
• Adverse Events (**)
 
• Echo (*)
 

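### Section 9.9.3.3 admits only in-window echoes to the follow-up form although no echo is scheduled, so freedom from SVD may read too high.

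*Combined protocol and SAP*

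**What the plan says.** Section 9.9.1 sets annual contacts: "Scheduled visits will occur yearly over 10 years after the implant date". They take place in the outpatient department "or, if not possible, by telephone contact with the patient". Table 1 in section 9.1 flags echo at every time point with the note "This is only when available", so no follow-up echo is mandated. It prints the yearly window as "<30 days >61 days". Section 9.9.3.3 then restricts what may be entered: "Provide follow-up echo data (echo date must be in the follow-up window". The pre-discharge echo in 9.8.1.2 carries no such date limit.

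Section 4.2.1.3 lists as a secondary endpoint: "Freedom from structural valve deterioration". Its analysis falls under the general statement in 8.3.1: "For the time to event data, survival analysis will be used to estimate the survival rate and 95% confidence interval". Nothing states which data source establishes SVD, which date counts as the event, or when a patient without an event is censored. For the primary endpoint the event date is explicit in 8.2.1: "The survival time will be calculated as the number of days from implant date to reoperation date due to SVD".

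SVD also has a route with no window. Structural deterioration is on the list of anticipated events in 9.2.2. Section 9.2.3 requires immediate reporting of all serious adverse events and all adverse device effects, allows entry as an unscheduled visit, and collects diagnostic test information.

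**The concern.** The study relies on echoes done in routine care, then asks that their dates fall in a study window that routine care has no reason to follow. An echo done five months after an anniversary is existing, dated evidence on valve function, yet it is not to be provided on the follow-up form.

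Two kinds of information are at risk. One is SVD that causes no symptoms, or that is visible on echo but not labelled an adverse event. It surfaces later, at an in-window echo or a reoperation, or not at all. The other is the normal echo, which shows how long a valve was known to be sound and which no adverse-event form will capture.

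Under a Kaplan-Meier analysis with no stated censoring rule, a patient with no admissible echo can count as free of SVD up to last contact. Because SVD persists once present, late or missed detection can only raise the estimate. Durability is the primary objective, and this endpoint is the plan's broadest measure of it.

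**Working it through.** The plan states no figure for echo frequency, echo timing or SVD detection, so there is none to reproduce. The check asks how much the window could matter.

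**1. Share of the year inside the window** (Table 1, read as 30 days before to 61 days after the anniversary).
- (30 + 61)/365.25 = 91/365.25 = 24.9% inside, 75.1% outside.
- Counting the anniversary day: 92/365.25 = 25.2% inside, 74.8% outside.

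**2. Share of echoes outside the window.** This equals 75% only if dates are uniform over the year. If dates are normal around the anniversary, the share outside is 1 − [Φ(61/SD) − Φ(−30/SD)]:
- SD 15 days: 2%
- SD 30 days: 18%
- SD 60 days: 46%
- SD 90 days: 62%

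**3. Effect on 10-year freedom from SVD, by simulation.** Inputs:
- Mortality from 8.1.2: 63.4% at year 10, so −ln(1 − 0.634)/10 = 0.1005 per year.
- Drop-out from 8.1.3: 20%, taken over 10 years, so −ln(0.80)/10 = 0.0223 per year.
- Assumed: true 10-year freedom of 90%, rising hazard (Weibull, shape 3).
- Assumed: one echo in 80% of years.
- SVD is counted at the first admissible echo after onset, or at an out-of-window echo that leads to an adverse-event (AE) report. Patients with no such finding run on event-free to death, drop-out or the end of follow-up.

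| Echo dates | AE capture of out-of-window findings | All echoes | Under the window rule | Shift (points) |
|---|---|---|---|---|
| Uniform | none | 91.9% | 96.3% | 4.4 |
| Uniform | 50% | 91.9% | 93.3% | 1.4 |
| Uniform | 90% | – | – | about 0.3 |
| SD 30 days | none | 92.0% | 92.7% | 0.7 |
| SD 60 days | none | – | – | 2.0 |
| SD 90 days | none | – | – | 2.9 |

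The capture rows give each out-of-window positive echo its own chance of being reported. If capture is instead a fixed trait of the patient, so that a missed case stays missed on later out-of-window echoes, the shifts are about 2.2 points at 50% and 0.4 at 90%. With an echo in 40% of years, uniform dates and no capture, the figures are 94.1% and 97.9%, a shift of 3.8 points.

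**4. Second model as a check** (constant hazard, no deaths, 10-year SVD incidence of 10% or 20%, echo in 30% to 100% of years). The shift is:
- 2.3 to 8.2 points with uniform dates and no capture;
- 0.2 to 1.2 points with SD 30 days and no capture;
- 0.1 to 0.4 points with uniform dates and 90% capture.

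**5. What the window does not explain.** With every echo used, the estimate in step 3 is still 91.9% against a true 90%, or 1.9 points high. With an echo in 40% of years it is 94.1%, or 4.1 points high. That part comes from echo being optional and from detection waiting for the next echo.

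**The case against.** The strongest reply is that 9.9.3.3 governs one form only. A positive echo at any date should lead to an event report under 9.2.2 and 9.2.3, with no window and with the test result attached. The yearly visit also asks about events since the previous one and may draw on hospital records. Moreover, outpatient attendance is the default and telephone the exception, so many echoes may be done at the visit and fall inside the window.

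Much of this stands. A reader might infer that three quarters of echoes are discarded and that freedom from SVD is therefore overstated by some four points. The documents do not support that. They nowhere say that an out-of-window echo is ignored for SVD, and 75% is a consequence of uniform timing, not a documented rate or a strict upper bound. Table 1's window is also not printed as a clear interval, so the 25% rests on one reading. The data-collection appendix to which 9.9.8 refers is not in the text available, so whether its forms accept unscheduled echoes cannot be checked.

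The reply does not remove the point. The event route works only when someone labels a finding as an event. The look-back at the yearly visit is put to the patient, who cannot report silent deterioration. Normal echoes never enter by that route. Default outpatient attendance does not make an echo part of the visit.

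**Conclusion.** The concern holds in a limited form. The rule withholds existing dated echo evidence from the follow-up form, and together with optional echo and no stated ascertainment rule for SVD it may delay or miss silent or unlabelled cases. The direction is upward in every scenario run. The size is not known. Under a true 90% freedom and an echo in 80% of years it runs from about 0.3 points (uniform dates, 90% adverse-event capture) to about 4.4 points (uniform dates, no capture), with about 0.7 if echoes cluster at the anniversary with an SD of 30 days and nothing is captured.

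A reader might extend this to the primary endpoint. That does not follow, because reoperation due to SVD is timed by the reoperation date and not by an echo. Only a secondary endpoint with no success criterion is touched. Nor is the window the whole source of upward bias: optional echo leaves some in place after the rule is removed. The change is still worth making because it uses data that already exist and can only reduce late or missed detection.

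**What to change.** - **Section 9.9.3.3:** remove the date restriction. Enter every existing echo done since the last contact, with its actual date. In-window echoes can still be used for haemodynamic summaries by visit.
- **Table 1:** print the yearly window as a clear interval around the anniversary.
- **Section 8.3.1:** date SVD from the first echo or event report that shows it, and state the censoring rule for patients without SVD.

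The cost is protocol and form wording and a few more existing echo reports to enter. No additional echo is asked for. Off-schedule echoes may be symptom-driven, and the report should say so.

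Censoring at the last echo might be offered as a lower bound for freedom from SVD. It should not be a required result, because it thins the risk set just before year 10 and can fall below the true value. At most it is a labelled sensitivity analysis with the number at risk shown.

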## **10 RISK DESCRIPTION AND MINIMIZATION**

### **10.1 POTENTIAL BENEFITS**

Potential benefits to the patients may include, but are not limited to, relief of valvular stenosis and/or incompetence and related symptoms. A patient may benefit from the improved longevity of the valve, due to the Linx™ treatment of the Trifecta valve (if the Linx™ treatment is proven effective). The patient will be monitored throughout the duration of the clinical study. Patients will be evaluated at pre-determined time points to assess their status. In addition, similar benefits may accrue to future subjects through experience gained in this clinical study.

### **10.2 POTENTIAL RISKS**

It is expected that the study related procedures: clinical assessment and the determination of the NYHA classification entail no additional risks to the patient other than those commonly associated with the follow-up of patients who have had a prosthetic heart valve implanted.

## **11 ETHICAL BASIS**

This investigation will be performed in accordance with the World Medical Association Declaration of Helsinki (appendix C), ISO 14155 and all local legal and regulatory requirements.

Prior to the start of the investigation, the clinical investigational plan will be submitted together with its associated documents (patient information sheets, patient informed consent forms in the local language) to the relevant Ethics Committee (EC) / Institutional Review Board (IRB) for review.

EC/IRB approval document should clearly identify

- the date of the meeting,
- constitution of the committee and voting members present at the meeting
- the approved version of the clinical investigational plan CIP
- the approved version of the patient information and informed consent.

Approval from the EC/ IRB is necessary prior to the start of the investigation. The original approval is to be filed in the Investigator Study Binder and a copy of the approval is provided to St. Jude Medical prior to the first investigational assessment.

Any amendments to the protocol should be submitted to the relevant EC/IRB.

EC/IRB will be informed about SAEs and UADEs in accordance with local and national requirements.

## APPENDIX A: ABBREVIATIONS

Abbreviation	Description
ACC	American College of Cardiology
ADE	Adverse Device Effect
AE	Adverse Event
AF	Atrial Fibrillation
AHA	American Heart Association
AVR	Aortic Valve Replacement
CA	Competent Authority
CABG	Coronary Artery Bypass Grafting
CIP	Clinical Investigation Plan
CPL	Clinical Projects Leader
CRA	Clinical Research Associate
CV	Cardiovascular
CRF	Case Report Form
EC	Ethics Committee
eCRF	Electronic Case Report Form
FU	Follow Up
INR	International Normalized Ratio
IFU	Instruction for Use
IRB	Institutional Review Board
ISB	Investigator Study Binder
PIC	Patient Informed Consent
SAE	Serious Adverse Event
SMF	Site Master File
SOP	Standard Operating Procedures
SVD	Structural Valve Deterioration
SJM	St. Jude Medical

